Economic analysis. Economic analysis is based on cost-effectiveness analysis (CEA), in which the alternative interventions are examined in the light of total cost per unit of health outcome. Incremental cost-effectiveness ratios will be calculated for the different frailty profiles, as the cost incurred to prevent one event, given that there was a significant reduction in the primary and secondary end-point, all-cause- and HF-related admissions, non-HF related admissions between groups. The time horizon will be equivalent to that observed during the period of the study (ie, no future projections are made). Moreover, a cost-utility analysis is programmed, calculating quality-adjusted life years (QALY) for each intervention group using the survival method and EuroQOL index as utility. To examine the impact of change in one or more variables on the results of the analysis, a sensitivity analysis where the cost of DMP and hospitalizations are changed of $\pm 10\%$ will be performed.

Study sample.

Based on previous studies (5,6), metanalyses (7-10) and national databases (3), the study sample is calculated to detect at least a 40% relative reduction at two years in the outcome of death and/or unplanned readmission for heart failure in the DMP, based on the assumption of a 60% event rate for the control group with a 0,05 alpha and 0,90 power. The planned sample size is at least 92 patients per group or, alternatively, the occurrence of 88 events.

Statistical Analysis.

In the primary Study, the two groups will be compared by the t test for normally distributed continuous variables and the chi square test for normal variables (with calculation of odds ratio [OR] and 95% confidence intervals [CI] where appropriate) and the Fisher exact test for variables with a prevalence <5%. Analyses are conducted according to an intention-to-treat approach. Kaplan-Meier survival curves are constructed to assess differences in deaths or readmissions between groups and compared using the log rank test. Data for all event-free patients are censored on study day 730. Event-free survivals are tested with the Cox proportional hazards method. Logistic regression analysis will be performed in order to identify factor potentially related to non-adherence to the program.

In the Secondary Study: Groups will be compared by the t test for normally distributed continuous variables (with Bonferroni correction as appropriate) and the chi square test and Fisher exact test for

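### The cost per event prevented is to be calculated only where the event reduction is significant, which on average overstates the effect in the ratios that are reported

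*Protocol*

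**What the plan says.** The Economic analysis section of the protocol states: "Incremental cost-effectiveness ratios will be calculated for the different frailty profiles, as the cost incurred to prevent one event". The same sentence then sets a condition, "given that there was a significant reduction in the primary and secondary end-point", goes on to list types of admission, and ends by referring to a comparison between groups.

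Two further items follow in that section. One is "Moreover, a cost-utility analysis is programmed, calculating quality-adjusted life years (QALY) for each intervention group", which has no significance condition. The other is "a sensitivity analysis where the cost of DMP and hospitalizations are changed of" ±10%.

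Under Estimation of costs, the protocol also plans costs stratified by frailty level. The list of collected variables includes mean costs with standard deviations and the mean saving per patient. None of these depends on a significant result.

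The design figures stand under Study sample: "the study sample is calculated to detect at least a 40% relative reduction at two years", "based on the assumption of a 60% event rate for the control group with a 0,05 alpha and 0,90 power". The size follows: "The planned sample size is at least 92 patients per group or, alternatively, the occurrence of 88 events".

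**The concern.** A cost per event prevented is the cost difference divided by the event difference. If it is computed only when the event difference passes a significance test, samples with a large observed difference are kept and samples with a small one are dropped. Averaged over the ratios that survive, the denominator is too big and the programme looks cheaper per event than it is. The smaller the group tested, the larger the difference needed to pass, and the worse the distortion. Non-significance is no reason to withhold a ratio: cost and effect differences can still be estimated, with wide intervals.

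The Synopsis and Introduction name long-term cost-effectiveness as an open question, and the secondary aim is to learn which frailty profiles benefit most. Ratios that are too favourable in some profiles and absent in others would serve both purposes badly.

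**Working it through.** **Inputs from the protocol.** Control event rate 60%; relative reduction 40%, so 36% under DMP and a true difference of 0.24; alpha 0.05, taken as two-sided; power 0.90; 92 per arm or 88 events; HF admission tariff EUR 3184.26.

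**Reproducing the planned size.** Pooled two-proportion formula:

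n = [1.96·√(2·0.48·0.52) + 1.2816·√(0.60·0.40 + 0.36·0.64)]² / 0.24² = (1.385 + 0.879)² / 0.0576 ≈ 89 per arm.

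The arcsine formula gives 90. Power at 92 per arm is 0.909. Expected events are 92 × (0.60 + 0.36) = 88.3. The stated 92 per arm and 88 events are therefore consistent with the stated assumptions.

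**Effect of the filter.** Take binomial events in each arm and a two-sided chi-square test at 0.05 with DMP better. Average the observed difference over the samples that pass. Without the filter, the expected difference is the true one at any group size.

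| True difference | Patients per arm | Chance of passing | Mean difference if passed | Overstatement |
|---|---|---|---|---|
| 0.24 (40% relative) | 92 | 0.90 | 0.254 | 1.06 |
| 0.24 | 46 | 0.63 | 0.300 | 1.25 |
| 0.24 | 31 | 0.50 | 0.339 | 1.41 |
| 0.24 | 15 | 0.25 | 0.465 | 1.94 |
| 0.15 (25% relative) | 92 | 0.52 | 0.206 | 1.37 |
| 0.15 | 31 | 0.23 | 0.314 | 2.09 |

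The 92-per-arm rows describe a single trial-level test. The other rows describe testing within a half, a third or about a sixth of the trial. The protocol defines a six-stage frailty score but gives neither the grouping for the ratios nor any group size, so 46, 31 and 15 are assumptions.

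The 31-per-arm row can be checked by hand. With a pooled rate of 0.48, the difference needed to pass is about 1.96·√(0.48·0.52·2/31) = 0.249, already above the true 0.24.

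**From the event difference to the ratio.** With the cost difference held fixed, the ratio at 31 per arm is multiplied by 0.24/0.339 = 0.71. The cost difference is not really fixed, because admissions drive both cost and events. As an illustration, assume Poisson admissions matching 60% and 36% with at least one event. At 31 per arm the filter then raises admissions averted per patient from 0.47 to 0.60. With an assumed DMP cost of EUR 2000 per patient, the ratio falls from about EUR 2125 to about EUR 222 per event prevented. With an assumed EUR 1000, both values are negative (about −2046 and −2733) and no longer mean a cost per event.

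**What the ±10% change covers.** It moves unit costs, not the effect. At 92 per arm, the 95% sampling interval for a difference of 0.24 is 0.24 ± 1.96·√((0.24 + 0.2304)/92) = 0.10 to 0.38. For a fixed cost difference, that alone multiplies the ratio by 0.63 to 2.40.

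For costs, assume 0.6 HF admissions per control patient, 40% fewer under DMP, Poisson counts and a DMP cost of EUR 1000:

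- Mean cost difference: 1000 − 0.24 × 3184.26 = EUR 236.
- Range under ±10% on both costs: EUR 59 to 412.
- Standard error: 3184.26·√(0.96/92) = EUR 325, so the 95% interval is EUR −402 to 873, 3.6 times as wide.

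Over 0.6 to 1.0 control admissions and a DMP cost of EUR 1000 to 1500 (all assumed), the sampling interval at 92 per arm is 2.8 to 3.6 times as wide as the ±10% range.

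**The case against.** The strongest reply is that the condition may be a single test for the whole trial. Elsewhere in the protocol, groups usually means the two arms, while frailty strata are called profiles or subgroups. On that reading the overstatement at the design effect is only about 6%. This stands, so the within-frailty figures cannot be given as the size of the bias without saying which reading they assume. It does not remove the bias, which reaches about 37% under the same reading if the true relative reduction is 25%. The clause could also be read as meaning since rather than if, as the protocol mixes tenses. But the result was unknown when the plan was written, and a condition is the natural sense.

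A reader might also infer more than the text supports:

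- **That the economic results are suppressed wherever significance fails.** They are not. QALYs per arm, costs by frailty level and the mean saving per patient are unconditioned. Only the cost per event prevented is missing.
- **That every reported ratio must be too optimistic.** The bias is an average over ratios that pass; a single ratio may err either way.
- **That the ±10% change is the only uncertainty analysis.** The protocol states it without calling it the only one, and interval methods could stand in an analysis plan that is not shown. The absence of a bootstrap is therefore not a firm error. The significance condition is.
- **That cost per event is too low by a fixed 29%.** That figure needs 31 per arm and an unchanged cost difference, and neither is in the protocol.

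**Conclusion.** The significance condition on the cost per event prevented is a written rule and should go. It favours DMP on average under either reading of where the test is applied. At the design rates the event difference is overstated by about 6% for a trial-level test (about 37% if the true relative reduction is 25%), and by about 1.25, 1.41 and 1.9 times if tested within frailty groups of 46, 31 and 15 per arm. These results rest on a two-sided 0.05 chi-square test of the primary event. Requiring significance on further end-points as well was not modelled.

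The point is confined to a supporting economic analysis and leaves the primary end-point, the sample size and the main efficacy comparison untouched. Bootstrap intervals are a sensible addition, but on their own they would not cure selection among the ratios reported.

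**What to change.** In the Economic analysis section, delete the clause that makes the ratios depend on a significant reduction. State instead that incremental cost, incremental effect (events and QALYs) and the incremental ratio or net monetary benefit will be reported for the whole trial and, as exploratory, for each frailty group, regardless of p-values. State how the six frailty stages are grouped for this purpose. Net monetary benefit over a range of thresholds stays interpretable if DMP turns out both cheaper and better.

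Add 95% intervals from a patient-level bootstrap, resampling cost and effect together within arm. Keep the ±10% cost change as an additional price sensitivity analysis.

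The cost is a change of wording and a short program on data already planned for collection. The reported figures will be wider and, on average, less favourable to DMP.

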In both groups initial assessment will include history, physical examination and a multidimensional assessment (12) including education, marital status, financial income, social and emotional support, ability to perform basic (BADL) and instrumental (IADL) activities of daily living (13,14), cognitive status measure by means of the Folstein Mini Mental Status Examination, depressive symptoms measured by means of the Geriatric Depression scale, comorbidity will be quantified with the Charlson Comorbidity index (15), quality of life and self-perceived health, evaluated, respectively with the Minnesota Living with Heart Failure (MLwHF), a 5-item scale (from very good to very poor) and the EuroQOL (16). Disability is defined as an impairment in at least two IADL or at least one BADL.

An ad-hoc translated and validated local version of the European Self Care Behaviour scale (ESCB) will be administered in order to evaluate the baseline level of self-care (17). Frailty is measured by means of a modified frailty score (FS) (22), calculated combining five domains of functioning (age over 80, cognitive impairment defined as a MMSE score \leq 24, reduced mobility, urinary incontinence and physical impairment defined as a NYHA functional class III-IV) into six stages of increasing impairment. Stage 1 included patients <80 years, in II NYHA class and without impairments in mobility, continence, or cognitive function. Stages 2 to 6 included patients with the presence of one, two, three, four or all of the specific items, respectively. The risk profile of each patient will be also calculated by means of a prognostic score index .

Intervention

All patients will be discharged on optimized therapy and will receive before randomization a detailed summary and a standardized educational program focused on low-salt diet and drug therapy, self monitoring of blood pressure and symptoms, daily weight, smoke cessation, fluid intake and daily physical activity.

DMP Group. The program is based on a hybrid model, combining hospital clinic- and home-based care. In each of the two participating teams, the members will be a cardiologist experienced in geriatrics, two-to-four specialized nurses and the patient's primary care physician. According to ESC guidelines, the components of the program are: discharge planning, continuing education, therapy optimization, improved communication with health care providers, early attention to signs and symptoms and flexible diuretic regimen (11).

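### The primary-study analysis compares continuous outcomes by t test and names no covariate for its Cox model, so precision available from baseline scores already being collected is lost

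*Protocol*

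**What the plan says.** The Statistical Analysis section of the protocol sets out the primary study first. For continuous and categorical variables, "the two groups will be compared by the t test for normally distributed continuous variables and the chi square test for normal variables" (the second use of 'normal' evidently means nominal, the word in the Secondary Study paragraph). Deaths and readmissions are compared by Kaplan-Meier curves and the log-rank test, and "Event-free survivals are tested with the Cox proportional hazards method". No baseline value, covariate or stratum is named for any of these.

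The baseline data exist. Under Measurments: "In both groups initial assessment will include history, physical examination and a multidimensional assessment". That assessment includes MLwHF, a five-level health rating and EuroQOL; the same section defines the modified frailty score (stages 1 to 6). The Synopsis also says that the multidimensional assessment is done in all patients at baseline. Quality of life is a planned outcome under Objectives.

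Adjusted Cox models do appear, in the Secondary Study paragraph. Intervention groups and frailty subgroups are compared there with and without 13 clinical covariates. Age and NYHA class III-IV, two of the five frailty items, are on that list. Baseline quality of life and the frailty score as a covariate are not; frailty enters as a subgroup and interaction factor.

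**The concern.** When a score is measured at baseline and again at follow-up, a t test on the follow-up value leaves in the error term all the variation that the baseline value could explain. ANCOVA on the baseline score removes that part without needing more patients. The same reasoning applies, less strongly, to a Cox model when a prognostic factor such as frailty is known for everyone.

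At stake is precision: wider intervals and lower power for quality of life than the collected data allow, and a small forgone gain for the primary end-point. There is also a practical point. A covariate named in advance is not open to dispute, whereas one chosen after the data are seen is.

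**Working it through.** **1. The plan's own figure.** Inputs from Study sample: "based on the assumption of a 60% event rate for the control group with a 0,05 alpha and 0,90 power", and "at least a 40% relative reduction at two years in the outcome of death and/or unplanned readmission for heart failure". The result stated there: "The planned sample size is at least 92 patients per group or, alternatively, the occurrence of 88 events". Follow-up, from Statistical Analysis: "Data for all event-free patients are censored on study day 730". Sidedness is not stated; two-sided is assumed because it reproduces the figures.

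- DMP rate: 0.60 × (1 − 0.40) = 0.36.
- Hazard ratio under constant hazards: ln(0.64)/ln(0.40) = 0.487.
- Freedman events: (1.960 + 1.282)² × [(1 + 0.487)/(1 − 0.487)]² = 10.51 × 8.40 = 88.3.
- Patients per group: 88.3/(0.60 + 0.36) = 92.0.

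Both stated figures come out. A one-sided test would need 72 events. The planned 90% power therefore rests on an unadjusted log-rank test and does not depend on adjustment.

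**2. Quality-of-life scores.** The protocol gives no correlation r between baseline and follow-up scores, so the range is an assumption. Relative to a t test on follow-up values, the ANCOVA variance factor is 1 − r². The power column takes a difference that the t test would detect with 80% power at 92 per group: (1.960 + 0.842) × √(2/92) = 0.413 SD.

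| r | 1 − r² | Variance falls by | Power | n per group for 80% |
|---|---|---|---|---|
| 0.3 | 0.91 | 9% | 83.6% | 84 |
| 0.5 | 0.75 | 25% | 89.9% | 69 |
| 0.7 | 0.51 | 49% | 97.5% | 47 |

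The power and n columns suppose a score for all 92 per group. With deaths and missing scores the absolute figures change, but the variance factor does not.

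If the t test were applied to change from baseline instead, its variance factor with equal SDs at both times would be 2(1 − r): 1.40, 1.00 and 0.60. ANCOVA is still smaller at each r (0.91, 0.75, 0.51).

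**3. Primary end-point.** Simulation with 92 per group, marginal two-year rates of 60% and 36%, and 4,000 trials per row. The covariate is one normally distributed prognostic score standing in for frailty; its strength is an assumption.

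| Hazard ratio per SD of the score | Cox, no covariate | Cox, adjusted | Conditional treatment HR |
|---|---|---|---|
| 1.00 (no effect) | 91.3% | 91.5% | 0.487 |
| 1.35 | 91.8% | 92.9% | 0.477 |
| 1.65 | 91.3% | 94.4% | 0.459 |
| 2.0 | 92.3% | 97.2% | 0.433 |

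The gain is about 1 to 5 points where the score is prognostic and nil where it is not. With no treatment effect and a hazard ratio of 1.65 per SD, the type I error was 5.5% unadjusted and 5.4% adjusted.

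**The case against.** The strongest reply is that nothing here is wrong. Unadjusted comparisons in a randomised trial are valid, the sample size was built on one, and covariate lists are often left to a statistical analysis plan, which is not at hand. The Cox sentence is silent on covariates; it does not state that the model is unadjusted. The protocol also already plans an adjusted Cox comparison of the intervention groups, with age and NYHA class in it. All of this stands, and it limits the point to efficiency. It does not dispose of it: the t test is fixed by name, and the adjusted models sit in the Secondary Study without the covariates that matter here.

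Two further objections also stand and shape the fix.

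- **Timing.** The baseline assessment is not stated to precede randomisation. Only the discharge summary and education are. Under Eligibility, consent rests on information about the allocated group, so self-reported scores could be given after a patient knows the strategy.
- **Follow-up scores.** For usual care, the Intervention section describes six-monthly phone calls for vital status and events, and does not say that quality-of-life scores are repeated. The t test sentence does not name those scores or say whether changes are compared.

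A reader might go further and infer three things that the protocol does not support:

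- **That chance imbalance in frailty could create an effect.** The test's error rate already allows for such imbalance, as the type I error figures show.
- **That adjusting for clinic would add power.** It does so only if clinic predicts outcome, and no stratified randomisation is described.
- **That the primary result will be reported as an odds ratio.** The odds ratio is attached to chi-square comparisons, where appropriate, and the primary end-point has its own time-to-event methods.

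**Conclusion.** The point holds as a loss of precision. It is clearest for quality of life, where ANCOVA would cut the variance of a follow-up comparison by 9% to 49% for correlations of 0.3 to 0.7, provided that follow-up scores exist in both groups. For the primary end-point the gain is modest: about 1 to 5 points above a power that already meets the plan's 90%, for a prognostic score with a hazard ratio of about 1.35 to 2.0 per SD. Both ranges are assumptions, and the second uses a continuous score in place of the six frailty stages.

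It would be tempting to conclude that the primary analysis is underpowered or biased for want of adjustment. The protocol's figures say otherwise: 92 per group and 88 events follow from an unadjusted log-rank design.

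**What to change.** - **Quality of life (MLwHF, EuroQOL).** Where follow-up scores are obtained in both groups, replace the t test with ANCOVA on the baseline score.
- **Primary end-point.** Keep the log-rank test, on which the sample size rests. Pre-specify alongside it a Cox model adjusted for baseline frailty stage, with the form of the term fixed in advance.
- **Timing.** Use as covariates only baseline values recorded before the allocation is known, and say so.

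The cost is wording, since the baseline variables are already planned. One small downside should be stated in the plan: the adjusted hazard ratio is conditional and lies slightly further from 1 than the marginal one (0.477 to 0.433 against 0.487 in the scenarios above), so the two should not be read as the same quantity.

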
A written list of recommendations, a weight chart, a contact number available 6 hours/day and an educational booklet will be provided only to these patients. They will be encouraged to present their discharge/visit summary and weight chart at all visits. Follow-up is based on hospital clinic visits, periodical nurse's phone calls and home or office primary physician visits.

The cardiologists are the case managers, designed and documented the treatment plan. Hospital visits will occur in the heart failure clinics within 7 to 14 days from discharge and, therefore at 1, 3 and subsequently each 6 months. At each visits patients will receive reinforcement of education and optimization of therapy. Nurses will made follow-up phone calls to patients, receive the patient's calls and contacted patients when they did not present to scheduled visits. They could not modify therapy, however, they could recommend that the patient consults the cardiologist or primary care physician when the patient's status deteriorated abruptly or the patient experienced a significant problem

requiring prompt attention. The nurses also play a pivotal role in education program and coordination of patient's management. The primary care physicians are asked to assess adherence to treatment, evaluate possible adverse drug reactions and identify and possibly treat at home signs of worsening clinical condition, concurrent infections or comorbidities and potential precipitating factors, as well as dietary regimen. They will manage all problems not related to heart failure, receive regular written updates from the hospital team and will be notified of abnormal laboratory and clinical values.

Usual care. After discharge, patients assigned to UC will receive all treatments and services ordered by their primary care physician and/or personal cardiologist. The baseline clinical evaluation and therapeutic plan are documented in the patient's chart. In this group vital status and events are recorded by means of phone calls performed every six months.

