Outcomes. Patients will be followed for at least two years and outcome data will be obtained at every visit. All in- and outpatient activities are monitored through medical records and contacts with primary care physicians. All patients were followed for two years and clinical status, medications, number of primary care and specialist visits and events were recorded at each visit or phone call. Events were collected also using phone calls, hospital and administrative databases . Outcomes are evaluated in a blinded manner by a central endpoint committee composed of three cardiologists, who have no knowledge of the treatment assignment. Two members will independently evaluate all cases. In the event of a discrepant classification, the third member reviews the report and assigns the final classification. All MA questionnaires will be analyzed in a blinded fashion.

Estimation of costs. In this study the National Health System (NHS) perspective will be adopted, as in Italy it provides all health care services for patients affected by moderate-to-severe HF. Data on resource utilization will be collected prospectively and will only comprise direct costs (pre-discharge education, medications, management program and usual care and hospitalizations) calculated on the basis of NHS charges at the time of the study and stratified according to the level of frailty. The costs of the hospital-based outpatient program are derived on the basis of the total of telephone calls (mean 15 minutes each) and visits (mean 30 minutes each). The average cost for one HF hospitalization, according to standard mean tariff for Diagnosis-Related Group (DRG) 127 at the time of the study is € 3184.26. For non-HF related admissions, individual DRG tariffs will also be calculated. The initial admission is not included in the cost analysis.

The costs of daily medical therapy (digitalis glycosides, diuretics, beta-blockers, calcium channel blockers, other vasodilators, anti-arrhythmic drugs, ACE inhibitors, angiotensin receptor blockers and anticoagulants), will be estimated using the average dose of therapy to calculate the number of tablets

taken during the follow-up and multiplying this number by the cost per tablet reported in the annual National Therapeutic Formulary. These costs will be actualized by assuming an annual rate of increase of 5%. Indirect costs are difficult to evaluate and will not be considered.

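### The day-730 censoring rule makes no exception for event-free patients lost or withdrawn earlier, so read literally it credits them with unobserved event-free time

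*Protocol*

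**What the plan says.** The Statistical Analysis section of the protocol plans Kaplan-Meier curves, a log-rank test and Cox models under intention to treat. It fixes the censoring date in one sentence: "Data for all event-free patients are censored on study day 730". No other date is given for a patient who is lost or withdraws.

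The Outcomes section sets the length of follow-up: "Patients will be followed for at least two years and outcome data will be obtained at every visit". It then says, in the past tense, "All patients were followed for two years and clinical status, medications, number of primary care and specialist visits and events were recorded". It also names sources that do not depend on seeing the patient: "Events were collected also using phone calls, hospital and administrative databases".

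Contact differs by arm. For usual care (UC), the protocol says "In this group vital status and events are recorded by means of phone calls performed every six months". The disease management programme (DMP) arm has scheduled clinic visits, nurse calls, and nurses who contact patients who miss a visit.

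The Study sample section sizes the trial "to detect at least a 40% relative reduction at two years in the outcome of death and/or unplanned readmission for heart failure", "based on the assumption of a 60% event rate for the control group with a 0,05 alpha and 0,90 power". It concludes: "The planned sample size is at least 92 patients per group or, alternatively, the occurrence of 88 events".

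**The concern.** A censoring rule matters only for patients whose follow-up falls short, and here it gives the wrong date for them. An event-free patient lost on day 100 would enter the analysis as event-free to day 730. That patient would stay in the risk set for 630 days in which an event could not have been recorded.

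The effect is to lower the estimated two-year risk in any arm with losses. If losses are equal, the relative effect barely changes. If they differ, the arm with more loss looks better than it is. Unequal loss is possible because the two arms are followed by different means.

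A smaller matter lies next to it. The sample-size sentence offers an event count as an alternative to a number of patients, while the Outcomes section promises every patient at least two years. The protocol does not say how the two relate.

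**Working it through.** **1. The plan's own figures.** Inputs from Study sample: UC risk 0.60; 40% relative reduction, so DMP risk 0.60 × 0.60 = 0.36; alpha 0.05 (taken as two-sided, since sidedness is not stated); power 0.90.

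- Pooled two-proportion formula: n = 2 × 0.48 × 0.52 × (1.960 + 1.282)² / 0.24² = 91.06, so 92 per group.
- Expected events with full follow-up: 92 × 0.60 + 92 × 0.36 = 55.2 + 33.1 = 88.3, so 88.

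Both figures reproduce. The 88 events are therefore what 92 per group yields over two complete years. They are not a separate design.

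**2. Effect of the literal rule on the two-year risk.** The loss rates here and below are assumptions, because the protocol gives none. Assume exponential event times, a fraction L of patients with a loss time uniform over two years, no event captured after loss, and lost event-free patients set to day 730. With two-year risk p and Λ = −ln(1 − p), the Kaplan-Meier risk under the rule is

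(1 − L) × p + L × (1 − p/Λ).

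For UC, Λ = 0.916 and 1 − p/Λ = 0.345. For DMP, Λ = 0.446 and 1 − p/Λ = 0.193. The implied hazard ratio is 0.446/0.916 = 0.487.

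| Loss UC / DMP | UC risk | DMP risk | Relative reduction |
|---|---|---|---|
| 0 / 0 | 60.0% | 36.0% | 40.0% |
| 5% / 5% | 58.7% | 35.2% | 40.1% |
| 10% / 10% | 57.5% | 34.3% | 40.2% |
| 20% / 5% | 54.9% | 35.2% | 35.9% |
| 0 / 10% | 60.0% | 34.3% | 42.8% |

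Example, UC at 10%: 0.90 × 0.60 + 0.10 × 0.345 = 0.575. Equal loss lowers both risks and leaves the relative reduction almost unchanged. Unequal loss moves it in either direction.

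**3. Effect on the log-rank and Cox results.** Simulation under the same assumptions, 92 per arm, comparing the literal rule with censoring at the loss date:

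- 5% in both arms: power about 0.91 either way.
- 10% UC, 3% DMP: hazard ratio about 0.51 against 0.485; power about 0.87 against 0.91.
- 3% UC, 10% DMP: hazard ratio about 0.47 against 0.49, so the benefit is overstated.
- No true effect (60% in both), 20% UC and 5% DMP: two-sided error about 7%. Nearly all of it lies on the side where UC, the arm with more loss, looks better. In one run of 20,000 trials the 7.4% split into 6.7% false harm and 0.7% false benefit for DMP.
- No true effect, 10% UC and 3% DMP: error 5.4%.

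**The case against.** The strongest reply is that the plan leaves nobody to whom the bad rule would apply. Every patient is to be followed for two years. Death and heart-failure admission, the two parts of the primary endpoint, can be found in hospital and administrative databases without reaching the patient, so someone who stops answering calls is not automatically unobserved. This stands as a limit on size: the calculations assume no capture after loss and are therefore at the pessimistic end. It does not rescue the sentence. The protocol does not say that the databases cover every patient to day 730, and a censoring rule exists for the cases where follow-up fails.

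A second reply is that dates for lost patients are commonly left to the statistical analysis plan. That would hold if the protocol were silent. It states a rule for all event-free patients, and a later plan that censored at last contact would contradict it.

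A third reply concerns direction. If UC loses more patients, the bias runs against the programme, so false claims of benefit become rarer. That is true for that pattern only. The protocol does not establish which arm would lose more, or that either would.

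A reader might also infer that the trial could stop at the 88th event, with patients short of two years credited to day 730, or that the investigators could choose between an 88-event result and a full-follow-up result and so inflate the type I error. The documents do not support this. The 88 events appear only as a statement of size. No data cut-off, interim look or stopping rule is described, and stopping there with patients short of two years would break the two-year minimum.

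**Conclusion.** The point holds as a wrongly worded rule for the primary time-to-event analyses. It is not evidence that unobserved time will in fact be credited: with complete two-year ascertainment the rule does no harm. With incomplete ascertainment, equal loss hardly matters, while moderate unequal loss shifts the hazard ratio by about 0.02 in either direction. In the 10% and 3% case it costs about 4 points of power. A two-sided error near 7% needs a loss pattern as unequal as 20% and 5%. All of these sizes rest on assumed loss rates, exponential event times, uniform loss times and no capture of events after loss.

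The clause offering 88 events as an alternative is ambiguous beside the two-year minimum and should be reconciled with it. The figures of 92 and 88 are themselves correct. Severity: should fix.

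**What to change.** Replace the censoring sentence with a rule of this kind: each event-free patient is censored at the earlier of day 730 and the last date on which event-free status was ascertained, whether by contact, medical records or databases, with the date defined the same way in both arms. A patient whose status is confirmed from databases through day 730 is still censored at day 730, so nothing changes where follow-up is complete. The remaining assumption, that loss is unrelated to prognosis, is the usual one for these methods.

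In Study sample, state at least 92 per group as the planned size and 88 as the number of events expected from it. Remove the alternative wording or reconcile it with the two-year minimum, so that the study has one end rule.

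The cost is two sentences. The sample size does not change. The sponsor gives up any reading under which an event count alone could end the study.
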